#### 8.1.2. Adverse events

Adverse events will be assessed throughout the study as detailed in Section 8.4.

New onset of suicidal ideation will be considered an AE. Suicidal ideation will be assessed during every in-person visit using the C-SSRS and clinical assessment during participant interviews. The C-SSRS was developed by researchers at Columbia University and is widely used in clinical and research settings (https://cssrs.columbia.edu/). Significant suicidal ideation is endorsed on items 4 or 5 on the C-SSRS.

# 8.2. Efficacy Assessments (Secondary and Exploratory Endpoints)

Planned time points for the efficacy assessments are provided in the SoA (Section 1.3).

All efficacy assessments measured by questionnaires or surveys will be collected electronically for inclusion in the electronic data capture (EDC) database.

# 8.2.1. Patient Reported Outcomes (Secondary Efficacy Endpoints)

## **8.2.1.1.** Aggregate Worst Pain Score Change

To evaluate the efficacy of oral TRP-8802 to treat chronic pain symptoms in patients with FM, the aggregate worst pain intensity (0 to 10) on the PI-NRS at baseline (Days 1 to 7) will be compared to the 7 day (Days 57 to 63) aggregate immediately prior to the EOT visit (Day 64).

Pain will be measured daily using an electronic pain diary. Participants will receive a message via text or email at 6pm each evening with the PI-NRS questions. If the participant does not respond within 2 hours, a reminder text or email will be sent at 8pm. Response options will be closed at midnight. Participants who miss a day will be contacted the following day to remind them to complete their daily diary.

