**Table 1: Overview of Objectives and Endpoints** 

| Objectives   | Endpoints  |
|--|--|
| Primary  |  |
| To assess the safety of TRP-8802 under the conditions of this trial  | Safety during dosing sessions: vital signs (HR, BP), AEs Safety during trial: AEs  |
| Secondary  | Safety during trial. ALS   |
| To evaluate the clinical benefit of oral TRP-8802 in concert with psychotherapy to treat chronic pain symptoms in patients with FM | Aggregate weekly worst pain score change from Baseline (Days 1 to 7) to End of Therapy visit (Day 64) on a pain intensity numeric rating scale (PI-NRS) 11-item pain scale |
| To assess other potential therapeutic effects of TRP-8802 in conjunction with psychotherapy on FM symptoms                         | Participant self-reported outcomes:      pain interference     sleep     chronic pain acceptance     Patient Global Impression of Change (PGI-C)                           |
| Exploratory  |  |
| To characterize other TRP-8802 clinical and PD effects   |  |

AEs=adverse events; BP=blood pressure; FM=fibromyalgia; HR=heart rate; PD=pharmacodynamic; PROs=patient reported outcomes.

Note: The aggregate weekly pain score is over a 7-day period.

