## 4. Study Design

This is a single-arm, single center, open-label (uncontrolled) pilot study in participants with FM.

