## 4.1.3. Preparation Period (Visits 3 and 4, Day 11 and Day 18)

Participants will begin psychotherapy intervention, the structure of which has been used in previous psilocybin clinical trials. As with other psilocybin studies, discussions will include information on the participant's life history, current situation in life, as well as the participant's understanding, expectations, and intentions for the TRP-8802 administration sessions. In brief, during the approximately 8 hours of preparatory therapy at Visits 3 and 4, participants will develop rapport with two assigned therapists, learn about FM, as well as build comfort and

CONFIDENTIAL 25 27 February, 2024

understanding around the physical space and what will occur in the dosing sessions. Details of these sessions are provided in the Psychotherapy Manual. One of these preparatory therapy sessions may occur via a HIPAA-compliant video conferencing platform if necessary.

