## 6. Study Intervention(s) and Concomitant Therapy

In this protocol, study intervention is the combination of the investigational TRP-8802 and psychotherapy. This Section covers the administration of TRP-8802; psychotherapy treatment is covered in more detail in the Psychotherapy Manual.

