## 9.4.3. Secondary Endpoints (Efficacy)

The results of secondary endpoints will be shown at the baseline and each follow up visits based on Full Analysis Set Population and the PP Population. Pain score, pain interference, sleep disturbance, chronic pain acceptance, and the patient global impression of change were chosen as secondary measures given their relevance to FM symptom management (Clauw 2014; Williams 2011; Kratz 2007; Farrar 2001).

Aggregate worst pain score change from baseline to EOT (Day 64) will be measured on the 11-item PI-NRS. Average daily pain score will be measured from Day 1 to 7 (baseline) versus the 7 days immediately before EOT (Days 57 to 63). Changes in the worst pain intensity from the baseline through EOT will be presented in Full Analysis Set Population and the PP Population. A 30% or 2-point decrease in aggregated worst pain scores at either movement or rest will be considered a clinically significant response (Farrar 2001).

Pain interference is the degree to which pain affects important aspects of an individual's life, such as social, cognitive, and physical activities. The pain interference and its change from the baseline will be shown at the baseline and each follow up visit. Sleep disturbance includes assessment of sleep quality, perceived ability to fall and stay asleep, satisfaction of sleep, and depth of sleep. Sleep disturbance and its change from the baseline will be reported as well. In addition, chronic pain acceptance will be presented at baseline and follow up. Finally, patient impression in clinical status change will be shown.

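### The pain baseline is fixed at Days 1 to 7, but Visit 3, when psychotherapy begins, may fall as early as Day 4, so the baseline can include days after the study intervention has started.

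*Combined protocol and SAP*

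**What the plan says.** The pain endpoint is anchored to calendar study days. Table 1 in the Synopsis defines it as "Aggregate weekly worst pain score change from Baseline (Days 1 to 7) to End of Therapy visit (Day 64"). Section 8.2.1.1 repeats the window: the score "on the PI-NRS at baseline (Days 1 to 7) will be compared to the 7 day (Days 57 to 63) aggregate". Section 9.4.3 says "Average daily pain score will be measured from Day 1 to 7 (baseline) versus the 7 days immediately before EOT (Days 57 to 63"). None of the three ties the baseline to the date of Visit 3.

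Table 2 (Section 1.3) gives Visit 2 as Days 1 to 7, and Visits 3 and 4 as Days 11 and 18 with a window of ±7 days. Section 4.1 confirms that visits may use the windows in that schedule. Section 4.1.3, on the preparation period, says "Participants will begin psychotherapy intervention" and refers to what happens "during the approximately 8 hours of preparatory therapy at Visits 3 and 4". Section 6 states that "study intervention is the combination of the investigational TRP-8802 and psychotherapy".

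The pain diary is an evening measure: "Participants will receive a message via text or email at 6pm each evening with the PI-NRS questions" (Section 8.2.1.1).

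**The concern.** A change-from-baseline summary needs a baseline that precedes treatment. The pain objective in Table 1 concerns TRP-8802 given together with psychotherapy, so a diary day after the first therapy session is an on-intervention day for that objective. Yet the permitted dates for Visit 3 overlap the baseline week on Days 4 to 7.

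The design cannot absorb this elsewhere. Section 4 says "This is a single-arm, single center, open-label (uncontrolled) pilot study in participants with FM", so the within-person change is the whole of the efficacy evidence and no comparison arm shares the same baseline problem. If an early session lowers pain, the change is understated; if it raises pain, the change is overstated.

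Section 9.4.3 also counts a 30% or 2-point fall as a response, so a participant near that line could be reclassified. With about 10 participants, one reclassification moves the response rate by about 10 percentage points.

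**Working it through.** **Inputs from the documents.** Baseline Days 1 to 7 (Table 1, Sections 8.2.1.1 and 9.4.3). Visit 3 at Day 11 ±7, and Dose 1 at Day 22 ±3 (Table 2). Diary prompt at 6 pm (Section 8.2.1.1). About 10 participants (Section 9.2).

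**Step 1: permitted dates.** Earliest Visit 3 = 11 − 7 = Day 4; latest = 11 + 7 = Day 18. That is 15 permitted days, of which 4 (Days 4 to 7) lie in the baseline week. This is a count, not a probability. Earliest Dose 1 = 22 − 3 = Day 19, well after Day 7.

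**Step 2: overlap.** For Visit 3 on day v (4 to 7), the baseline ratings are: before the visit day, v − 1; on or after it, 8 − v; strictly after it, 7 − v.

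| Visit 3 on | Before | On or after | Strictly after |
|---|---|---|---|
| Day 4 | 3 | 4 (57%) | 3 (43%) |
| Day 5 | 4 | 3 (43%) | 2 (29%) |
| Day 6 | 5 | 2 (29%) | 1 (14%) |
| Day 7 | 6 | 1 (14%) | 0 |
| Day 8 or later | 7 | 0 | 0 |

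Both counts are needed. A daytime session would come before that evening's rating, but Section 8.2.1.1 gives no recall period, so that rating may also cover hours before the session.

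**Step 3: size of the shift.** Assume that the aggregate is the 7-day mean and that the session changes every later rating by d points. The documents give no value for d; 0.5 to 1 is an assumption.

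- Visit day excluded, shift = d × (7 − v)/7. For Day 4: 0.5 × 3/7 = 0.21 and 1 × 3/7 = 0.43. For Day 7: 0.
- Visit day included, shift = d × (8 − v)/7. For Day 4: 0.5 × 4/7 = 0.29 and 1 × 4/7 = 0.57. For Day 7: 0.07 and 0.14.

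A Day 4 visit thus shifts that participant's baseline by 0.21 to 0.57.

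**Step 4: precision lost by using only the days before Visit 3.** Let s be the day-to-day SD, τ the SD of true change between participants, and nb the number of baseline days. With days taken as independent, 7 end-week days and n = 10:

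SE of mean change = √[(τ² + s²(1/nb + 1/7))/10].

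With assumed τ = 1.5 and s = 1.2:

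- nb = 7: √[(2.25 + 1.44 × 0.2857)/10] = √0.2661 = 0.516.
- nb = 3 for all 10 participants (everyone seen on Day 4): √[(2.25 + 1.44 × 0.4762)/10] = √0.2936 = 0.542, a rise of 5.0%.

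Over s from 0.8 to 1.6 and τ from 1.0 to 2.0, the smallest rise is 1.4% (s = 0.8, τ = 2.0) and the largest 13.2% (s = 1.6, τ = 1.0).

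**The case against.** The strongest reply is that the schedule relies on visit order, not on the literal windows. Read literally, Table 2 would let Visit 4 (Day 18 ±7, Days 11 to 25) fall after Dose 1 (Days 19 to 25), and let Visit 6 (Day 23 ±3, Days 20 to 26) precede Dose 1, although Section 4.1.4 places that visit on the day after dosing. The columns run baseline then preparation, and the Introduction describes phenotyping and diary before the intervention begins. This stands as evidence of intent, and nominal Day 11 respects it. It does not close the gap: order only puts Visit 3 after Visit 2, which Section 4.1.2 places on Day 1, and no text makes Visit 3 wait for the end of the diary week.

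It might also be said that the ±7 applies to Day 18 only. Table 2 uses the same layout for other paired visits, such as 120 and 204 ±7, and the revision history speaks of preparation sessions in the plural, so this reading is weak.

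Other parts of the reply stand. The material at Visit 3 is preparatory: rapport, education about fibromyalgia, and familiarity with the setting. The documents give no reason to expect it to move daily pain within days. Every early case still has 3 to 6 diary days before Visit 3, and Section 9.4 leaves the detail to a SAP still to be finalised, so most of the problem can be handled in the analysis.

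A reader might infer that the baseline is contaminated, that drug effect leaks into it, or that the pain result is biased in a known direction. The documents support none of these. The overlap is permitted, not shown to occur; Dose 1 cannot precede Day 19; and the sign of any session effect is unknown.

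**Conclusion.** The point holds as an inconsistency between the fixed baseline and the visit window. Following both as written can put up to 3 of 7 baseline ratings strictly after the first psychotherapy session, or 4 of 7 counting the visit day. The day counts rest on the documents alone. The shift of 0.21 to 0.57 points for a Day 4 visit rests on the assumed session effect, on its being immediate and constant, and on the aggregate being a 7-day mean; it applies per affected participant, not to the group mean. Visit 3 on Day 8 or later leaves the baseline untouched.

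Severity is minor to modest. The endpoint is secondary and summarised descriptively in a small uncontrolled pilot; the primary endpoint is safety, and no test or sample-size calculation depends on the pain change. It is worth correcting because the correction is cheap and needs no new data.

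**What to change.** (a) Reconcile the Visit 3 window in Table 2 with the Days 1 to 7 baseline in Sections 8.2.1.1 and 9.4.3, so that the documents say how the two relate when Visit 3 is early.

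(b) In the SAP, compute each participant's baseline from the Days 1 to 7 diary entries dated before the actual Visit 3. Report the number of days used per participant, and show the full Days 1 to 7 result as a sensitivity summary.

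The cost is about one sentence in each document. Anyone seen on Days 4 to 7 would have a baseline of 3 to 6 days instead of 7, which is noisier for that person, and the missing pre-session days cannot be added later. For the group the loss is small: even with all 10 participants seen on Day 4, the standard error of the mean change rises only from about 0.52 to 0.54 under the stated assumptions, and by 1% to 13% over the ranges tried. If nobody is seen before Day 8, the two summaries are identical and nothing is lost.

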#### **4.1.2. Baseline (Visit 2, Day 1)**

Assessments on Day 1 will be considered baseline assessments. On Day 1, participants will undergo a rigorous pain phenotyping assessment (i.e., deep phenotyping) as shown in the SoA (Section 1.3). A validated battery of patient reported outcomes includes the following:

• STOP-Bang (Chung 2016; Nagappa 2015) will be used to screen for sleep apnea which can interfere with sleep. The STOP-Bang questionnaire consists of 8 questions that assess risk of sleep apnea, including snoring, tiredness, whether anyone has observed the person stop breathing in their sleep, high BP, body mass index, age, neck circumference > 16 inches, and sex.

From this deep phenotyping session until the end of active intervention (28 days after final TRP-8802 dosing session), participants will complete a daily electronic pain diary to evaluate pain level on a scale of 0 to 10, on the Pain Intensity-Numeric Rating Scale (PI-NRS).

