## **4.1.6.** End of Therapy (Visit 13, Day 64)

The EOT assessment will occur approximately 28 days after the last dosing session, when participants will complete their final deep phenotyping session. Regardless of whether or not a participant completes both dosing sessions or chooses to discontinue the study early, participants will be asked to complete all EOT and follow-up assessments if they have received at least 1 dose of TRP-8802.

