## Cuff Pressure Pain

Large volume, deep muscle pressure sensitivity (Graven-Nielsen 2015, Izumi 2014) will be assessed using an MRI-compatible rapid cuff inflator (Hokanson, Bellevue, WA) (Loggia 2012, Polianskis 2002, Polianskis 2001). This system includes an air compressor, computerized pressure controller, and a 13.5 cm by 82.5 cm Velcro-adjusted pressure cuff. Participants will first receive an ascending series of cuff pressures, starting at 20 mm Hg to 40 mm Hg and increasing in 20 mm Hg steps (10 second pressures, 20 second intervals) to tolerance or a maximum of 400 mm Hg. Each pressure will be rated after deflation on a 0 to 100 NRS. These pain ratings will be used to interpolate a series of eight tolerable cuff pressures that will be delivered in pseudo-randomized order and rated individually on pain intensity and unpleasantness. Stimulus response curves will be constructed for each participant and used for analysis, along with several derived variables: cuff-PPT, cuff-Pain50, and cuff-tolerance. In addition, tonic pain induced by continuous cuff pressure will be assessed (tonic-cuff). Each participant's individually calibrated Pain40-60 pressure (i.e., pressure that evokes a 40 to 60/100 pain rating) will be applied for 6 to 8 minutes to one gastrocnemius muscle. Pain intensity and unpleasantness ratings will be obtained every 60 seconds. This tonic cuff procedure will also be performed during fMRI.

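### The baseline worst-pain week contains the painful deep-phenotyping session and the End of Therapy week is planned to end just before it is repeated, so improvement may be overstated

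*Combined protocol and SAP*

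**What the plan says.** Section 8.2.1.1 uses worst pain on the 0 to 10 PI-NRS and says that the aggregate "at baseline (Days 1 to 7) will be compared to the 7 day (Days 57 to 63) aggregate immediately prior to the EOT visit", planned for Day 64. Section 4.1.2 places the baseline session at the start of the first of these weeks: "On Day 1, participants will undergo a rigorous pain phenotyping assessment (i.e., deep phenotyping) as shown in the SoA". There are no diary entries before it, because the diary runs "From this deep phenotyping session until the end of active intervention". Ratings are collected late in the day: "Participants will receive a message via text or email at 6pm each evening with the PI-NRS questions", with entry closing at midnight.

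The session is meant to produce pain. Section 8.2.3.1 (Cuff Pressure Pain) describes a first series of pressures "increasing in 20 mm Hg steps (10 second pressures, 20 second intervals) to tolerance or a maximum of 400 mm Hg", then eight more pressures, then 6 to 8 minutes of tonic pressure at a level rated 40 to 60 out of 100. Section 8.2.3.2 and Table 6 add, as proposed MRI content, two 5-minute scans under tonic cuff pressure at a level rated 30 to 50. At the EOT visit "participants will complete their final deep phenotyping session" (section 4.1.6), and Table 2 marks QST and fMRI at both visits.

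Four other details matter:

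- Table 2 gives Visit 2 as Days 1 to 7, and section 8.2.3.2 sets scanner pressure from a behavioral visit. QST and MRI may therefore fall on different baseline days.
- Table 2 gives the EOT visit as Day 64 ±3.
- Section 9.4.3 mentions an average daily score, while the endpoint is otherwise called an aggregate worst score.
- Section 9.4.3 counts a decrease of 30% or 2 points as a clinically significant response.

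**The concern.** The two weeks are not alike. One contains a day, possibly two, of deliberately provoked pain; on the planned schedule the other contains none. The diary asks for worst pain, and its prompt normally arrives after a daytime session, so evoked pain could enter that evening's score and any soreness could enter later ones. Nothing in the documents drops the session day, asks participants to disregard evoked pain, or collects a pain week before the session. Section 6.3 acknowledges only that an open-label study leaves sources of bias.

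This is the first efficacy endpoint in Table 1, and it is a before-after comparison in a single arm. Any lift confined to the baseline week would read as improvement and count toward the response rule. Because every participant follows the same schedule, enrolling more people would not remove it. Section 9.2 says the study is to inform later trials, so an overstated change could carry into their planning.

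**Working it through.** **1. The windows.** Last planned dose Day 36 + 28 = Day 64. The seven days before Day 64 are Days 57 to 63, and Days 1 to 7 is also seven days, so the plan's figures reproduce. The baseline week holds at least one session day. The EOT week holds none if the visit is on Day 64.

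**2. The EOT visit window.** With ±3 days the visit can fall on Days 61 to 67. A week anchored to the visit on day v covers days v−7 to v−1 and never includes the session. A week fixed at Days 57 to 63 includes it when v is 61, 62 or 63, and excludes it when v is 64 to 67.

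**3. Shift of a 7-day mean.** If k days are raised by d points, the mean moves by d × k / 7. The documents give neither d nor k, so these values are assumptions.

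| k (days) | d (points) | Shift | Share of 2 points |
|---|---|---|---|
| 1 | 1 | 0.14 | 7% |
| 1 | 2 | 0.29 | 14% |
| 1 | 3 | 0.43 | 21% |
| 1 | 4 | 0.57 | 29% |
| 2 | 1 | 0.29 | 14% |
| 2 | 2 | 0.57 | 29% |
| 2 | 3 | 0.86 | 43% |

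Moving the mean by 2 points would take a rise of 2 × 7 / 1 = 14 points on one day, impossible on a 0 to 10 scale, or 2 × 7 / 2 = 7 points on each of two days.

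The 30% limb depends on the baseline level, and section 5.1 sets no minimum pain score. A shift alone meets 30% only if observed baseline is at or below shift / 0.30, which is 0.57 / 0.30 = 1.9 or 0.86 / 0.30 = 2.9. At an observed baseline of 4 the threshold is 0.30 × 4 = 1.2, and 0.57 is 48% of it.

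**4. If the aggregate is the weekly maximum.** The maximum moves only as far as the raised day exceeds the highest of the other six days, never by more than the rise itself, and scores stop at 10. For example, if the other six days peak at 7 and the session day goes from 6 to 8, a 2-point rise moves the maximum by 1.

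A simulation with no treatment effect shows the scale. Its assumptions, none from the documents, are a person mean of 7 (SD 1.2), day-to-day SD of 1.0 to 1.5, whole-number scores capped at 10, and rises of 1 to 3 points.

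| Aggregate and days raised | Spurious improvement (points) | False response |
|---|---|---|
| Maximum, none | 0.00 | 4% to 8% |
| Maximum, one | 0.15 to 1.14 | 8% to 35% |
| Maximum, two | 0.27 to 1.39 | 10% to 45% |
| Mean, one or two | 0.13 to 0.69 | at most about 5% |

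The simulated mean shifts fall below d × k / 7 where the cap at 10 bites.

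**5. Effect of leaving out the raised days.** In the same simulation the spurious change in the mean becomes 0.00. With a maximum, dropping one or two baseline days while keeping seven at EOT biases the change by about −0.08 to −0.23 points the other way; with equal numbers of days it is 0.00.

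**6. Room for a week before the session.** Table 2 footnote a requires screening within 42 days before Dose 1. Day 1 to Day 22 is 21 days, leaving 42 − 21 = 21 days before Day 1. A 7-day diary leaves 14 of these. If Dose 1 is on Day 25, the end of its window, 42 − 24 = 18 days remain, and 18 − 7 = 11.

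**The case against.** The strongest reply is that nothing shows the session raises diary pain. Section 8.2.3.1 says that QST is well tolerated by chronic pain patients. The ascending pressures last 10 seconds each, and tonic pressure is set at 40 to 60 out of 100 in QST and 30 to 50 in the scanner, which may not exceed a participant's ordinary worst pain that day. The wording and recall period of the diary item are not given, so participants may not count brief calf pressure at all. MRI content is only proposed and depends on MRI eligibility. The endpoint is secondary and descriptive, in a pilot of about 10 whose only stated hypothesis concerns safety, and section 9.4 leaves detail to a fuller SAP.

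Most of this stands, and it limits the size and certainty of the point. It does not remove the asymmetry: the first series does run to tolerance, and no text keeps that pain out of the baseline rating. A later SAP can drop days but cannot recover a pre-session week that was never collected.

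A reader might infer that the bias always occurs and always favours treatment. The documents do not support that: they give no carry-over, and a literal Days 57 to 63 would itself contain the session for visits on Days 61 to 63. A reader might also infer that under a weekly maximum the whole rise on the session day passes into the endpoint. That would require the session day already to be at least as high as every other day, with room left below 10.

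**Conclusion.** The concern holds in conditional form. The calendar asymmetry is certain on the planned schedule; the resulting overstatement is possible and its size unknown. Under the 7-day mean suggested by section 9.4.3, it is about 0.14 to 0.57 points for one day raised by 1 to 4 points, and 0.29 to 0.86 for two days raised by 1 to 3. These rises are assumptions. Within them the artefact cannot alone produce a 2-point response, and it meets the 30% limb alone only at very low observed baselines, but it could add to a real change near either threshold. It would matter more under a weekly maximum, which the text does not rule out. The plan should be changed because the correction is cheap and the design has no control arm to expose the problem. The point does not bear on the primary safety objective.

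**What to change.** 1. **Baseline week.** For participants not yet at Visit 2, switch on the automated diary during screening and define baseline as the seven days immediately before the first phenotyping session (QST or MRI, whichever comes first), within the limit of 42 days before Dose 1. Amend Table 1 and sections 4.1.2, 8.2.1.1 and 9.4.3, and add the diary to the screening column of Table 2.
2. **One definition for all.** If some participants already have only Days 1 to 7, do not mix two baselines in a sample of about 10. Use, for everyone, the mean of the baseline diary days without the QST and MRI day(s), and show the Days 1 to 7 result alongside. This removes pain felt on the session day but not any carry-over into later days, which only a pre-session week avoids.
3. **Aggregate.** State that it is the 7-day mean of daily worst pain, averaged over the days kept if session days are left out. If a maximum is preferred, both windows need equal numbers of days.
4. **EOT week.** Define it as the seven days before the actual EOT visit instead of fixed Days 57 to 63.

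The cost is protocol wording plus about seven more diary evenings per new participant, with correspondingly less slack in screening; or, under item 2, a baseline mean over slightly fewer days and so a little less precise.
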